#### TFLs Related to *C-cell Hyperplasia and C-cell Neoplasms*

Analysis	Additional Information
Summary of C-cell Hyperplasia and C-cell Neoplasms	By Treatment Group
Listing of C-cell Hyperplasia and C-cell Neoplasms	

#### **4.6.3.5.4. *CardioVascular (CV) Events***

CV events will be identified based on MACE events and SAE which will be reviewed by medical.

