Participants who develop serum calcitonin increases $\geq 50\%$ of the screening value AND an absolute value ≥ 20 pg/mL and < 35 pg/mL at Visit 7 (Week 26) will be asked to repeat the measurement within 1 month. If this repeat value is increasing ($\geq 10\%$ increase), the participant will be encouraged to undergo additional endocrine assessment and longer-term follow-up by an endocrinologist to exclude a serious adverse effect on the gland.

Participants with an increase in serum calcitonin $\geq 50\%$ of screening value AND an absolute value ≥ 35 pg/mL at Visit 7 (Week 26) will be recommended to immediately undergo additional endocrine assessments and longer-term follow-up by an endocrinologist.

For participants who require additional endocrine assessment because of increased calcitonin concentration per criteria provided in this section, data from the follow-up assessment will be collected in the specific section of the eCRF.

Cardiovascular Events

Vital signs (PR, systolic blood pressure [SBP], diastolic blood pressure [DBP]) will be monitored throughout the study, and 12-lead ECGs will be monitored per the SoA (Section 1.3). Any clinically relevant finding from vital signs and ECGs obtained before the first dosing of study intervention that results in a diagnosis should be recorded in the eCRF as a preexisting condition and medical history. Any clinically relevant finding from vital signs and ECGs that occurs after the first dosing of study intervention and results in a diagnosis should be recorded as an AE in eCRF. Cardiovascular events will be analyzed using preferred terms and abnormal ECG result.

Hypersensitivity Reactions

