9.4. Statistical Analyses

9.4.1. General Considerations

Statistical analysis of this study will be the responsibility of Lilly or its designee.

All tests of treatment effects will be conducted at a 2-sided alpha level of 0.05, unless otherwise stated, and all confidence intervals (CIs) will be given at a 2-sided 95% level.

Any change to the data analysis methods described in the protocol will require an amendment only if it changes a principal feature of the protocol. Any other change to the data analysis methods described in the protocol, and the justification for making the change, will be described in the SAP and the clinical study report. Additional exploratory analyses of the data will be conducted as deemed appropriate.

The primary efficacy assessment, guided by efficacy “estimand”, will be conducted using the EAS1/EAS2 to compare dulaglutide 1.5 mg with dulaglutide 0.75 mg. The “efficacy” estimand measures the benefit of treatment when taken as directed.

Unless specified otherwise, safety assessments will be guided by an estimand comparing safety of dulaglutide 1.5 mg with dulaglutide 0.75 mg, irrespective of adherence to study intervention or initiation of antihyperglycemic rescue therapy. Thus, the safety analyses will be conducted using the SS1 or SS2. Selected safety analysis (for example, hypoglycemia) may be conducted excluding data after initiation of another antihyperglycemic therapy.

Summary statistics for continuous measures will include sample size, mean, SD, median, minimum, and maximum. The analysis model to make comparisons among treatment arms relative to continuous measurements assessed over time will be a mixed-model for repeated measures (MMRM), with terms of treatment, visit and treatment by visit interaction, pre-study

OAM class (see stratification factors in Section 4.1), and baseline measurement as a covariate. An unstructured covariance matrix will model the relationship of within participant errors.

The Kaplan-Meier method will be used for estimation of cumulative event free survival rates over time, and Cox proportional hazards regression analysis will be used to compare hazard rates among treatments.

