#### **4.6. Safety Analyses**

All safety analyses will be conducted using both the SS1 and SS2 to assess the safety parameters through 26 and 52 weeks, unless otherwise stated.

In this study AESIs defined in the PROTOCOL (Section 8.3.3) are as follows:

- a. Hypoglycemia
- b. Severe, persistent hyperglycemia
- c. Pancreatitis
- d. C-cell hyperplasia and C-cell neoplasms
- e. Cardiovascular events
- f. Hypersensitivity reactions

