##### TFLs Related to Clinical Laboratory Evaluations

Analysis	Additional Information
Listing of Patients with Treatment Emergent Abnormal (3*ULN) Laboratory Results	
Listing of Patients with Treatment Emergent Abnormal (ULN and LLN) Laboratory Results	
Summary and Analysis of Numeric Laboratory Tests	By Treatment Group and Visit
Summary and Analysis of Abnormal Laboratory Results	By Treatment Group and Visit
Shift of Calcitonin from Maximum Baseline to Maximum Postbaseline	By Treatment Group
Summary of Percent Change in Lipid Measurements	By Treatment Group and Visit

Abbreviations: LLN=Lower Limit Normal; ULN=Upper Limit Normal.

Listing of Individual Laboratory Values would be created upon request.

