#### 4.6.3.4. Electrocardiograms (ECG)

Descriptive summary of ECG results (PR, QRS, QT, RR, mean heart rate, and corrected QT interval (QTcF)) will be created.

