##### TFLs Related to ECG

Analysis	Additional Information
Summary of ECG Results	By Treatment and Visit

Abbreviations: ECG = electrocardiogram.

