#### **TFLs Related to CV**

Analysis	Additional Information
Summary of Cardiovascular Adverse Events	By Treatment Group and PT
Listing of Cardiovascular Adverse Events	

Abbreviations: PT= preferred term.

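### The SAP builds the cardiovascular AESI outputs from MACE and medically reviewed serious events, drops the protocol's abnormal-ECG element, and neither declares nor justifies the change

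*SAP*

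**What the plan says.** Protocol 8.3.3 lists CV events among the adverse events of special interest (AESIs) and states how they will be handled: "Cardiovascular events will be analyzed using preferred terms and abnormal ECG result". Under the same heading, a clinically relevant vital-sign or ECG finding after first dosing that leads to a diagnosis goes into the eCRF as an adverse event, whether serious or not.

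SAP 4.6 adopts the protocol's list: "In this study AESIs defined in the PROTOCOL (Section 8.3.3) are as follows". SAP 4.6.3.5.4 then gives its own rule for CV events: "CV events will be identified based on MACE events and SAE which will be reviewed by medical". Two outputs follow from it: "Summary of Cardiovascular Adverse Events", shown by treatment group and preferred term, and a matching listing.

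ECG data are handled separately in SAP 4.6.3.4: "Descriptive summary of ECG results (PR, QRS, QT, RR, mean heart rate, and corrected QT interval (QTcF)) will be created". The only output there is "Summary of ECG Results", by treatment and visit.

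On changes of method that do not touch a principal feature, protocol 9.4.1 says that any such change "and the justification for making the change, will be described in the SAP and the clinical study report". SAP 4.1 places that justification in the clinical study report only. SAP 4.9, the section for changes to protocol-planned analyses, is marked not applicable.

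**The concern.** The SAP says its AESIs are those of protocol 8.3.3, but it fills the CV category by a narrower rule than the protocol describes. A reader of a table titled as a summary of CV adverse events would not know that it is restricted to MACE and serious events.

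The narrowing bears on this dose comparison. Protocol 2.2 explains that lower doses were studied first in Japan because pulse rate rose at 1.0 mg and 1.5 mg in an early study. Non-serious rate or rhythm diagnoses are therefore of natural interest in a comparison of 1.5 mg with 0.75 mg. They are also the kind of event that a MACE/SAE rule leaves out of the CV display.

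**Working it through.** No figure in the plan needs recalculating. The check is a comparison of texts.

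**1. Which events are selected.** The protocol names preferred terms and abnormal ECG result, with no restriction to serious events. The SAP names MACE and medically reviewed SAEs. Preferred term survives in the SAP as the row level of the table, but it no longer decides which events enter.

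**2. Tracing one event.** Take a non-serious rhythm diagnosis made from the Week 26 ECG.
- Under protocol 8.3.3 it is recorded as an adverse event, receives a preferred term, and falls within the planned CV analysis.
- Under SAP 4.6.3.5.4 it is neither a MACE nor an SAE, so it enters neither the CV summary nor the CV listing.
- Under SAP 4.6.2 it still appears in the general tables by system organ class and preferred term.

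**3. Whether the SAP rule can be reproduced.** The SAP does not define MACE. The protocol spells out a three-component MACE only when describing another study (2.2 and 4.3). The wording leaves open whether the medical review covers SAEs alone or MACE as well, and no criteria for it are given. Protocol 10.1.4 plans prospective adjudication for pancreatic events only. Elsewhere in SAP 4.6.3.5 a concrete source is named: reported-term text for severe hyperglycemia, adjudication for pancreatitis, and MedDRA terms or SMQs for C-cell, hypersensitivity, gastrointestinal and gallbladder events.

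**4. The abnormal-ECG element.** Counting planned outputs with an abnormal-result title:

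| Data | SAP section | Abnormal-result outputs |
|---|---|---|
| Laboratory | 4.6.3.1 | 3 (two listings, and "Summary and Analysis of Abnormal Laboratory Results") |
| Vital signs | 4.6.3.2 | 1 (a listing) |
| ECG | 4.6.3.4 | 0 |

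The ECG section summarizes parameters, and nothing links abnormal ECGs to the CV outputs.

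**5. Whether the change is recorded.** Neither 4.6.3.5.4 nor 4.9 gives a reason. SAP 4.9 is not conclusive alone, because the SAP does explain one change elsewhere: the switch of hypoglycemia rate model, in 4.1. No such explanation is given for CV events.

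**The case against.** The best defence is that the SAP elaborates the protocol rather than changing it. Protocol 8.3.3 gives no term list, protocol 9.4.1 leaves technical detail to the SAP, and protocol 9.4.4 promises AESI summaries only where appropriate. The CV table is still shown by preferred term, and the SAP does not say that MACE and SAEs are the only sources. Table specifications are in a separate document not available here.

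Part of this stands. The protocol sentence is short, and choosing a term list is proper SAP work. But elaboration does not explain the loss of the abnormal-ECG element, or a seriousness filter under a table title that does not mention one. The SAP names no other source for CV events. That SAP 4.1 assigns justification to the study report may explain why none appears, but it does not remove the protocol's requirement to give it in the SAP as well.

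A reader might go further and infer that a CV signal at 1.5 mg could go unreported. The documents do not support that:
- Non-serious CV events remain in the treatment-emergent tables, with Fisher's exact test between arms (SAP 4.6.2). This includes ECG findings that led to a diagnosis.
- Change in pulse rate is a named secondary safety endpoint. It is compared between arms by MMRM (protocol 9.4.4) and by subgroup (SAP 4.7.1.2), and abnormal vital signs are listed.
- ECG heart rate and QTcF are summarized by arm and visit.

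A reader might also infer from SAP 4.1, which allows outputs with no patients to be omitted, that the CV table is likely to vanish. The documents give no CV event rate, so that likelihood cannot be sized. Nor would it measure the non-serious events that are left out.

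**Conclusion.** The departure is real and should be corrected, but its reach is limited. The SAP replaces the protocol's basis for the CV AESI analysis with a MACE/SAE rule that is not fully defined, omits the abnormal-ECG element, and does not record the change.

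What is affected is which events appear in one summary and one listing, how those are labelled, and whether abnormal ECGs are reported by arm. The primary endpoint, the error rate and general safety reporting are untouched. The number of events left out cannot be estimated, because the documents give neither CV event rates nor a split by seriousness.

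The conclusion rests on taking SAP 4.6.3.5.4 at its word, so that events outside MACE and SAEs are not selected. If the separate table specifications select more widely or include an abnormal-ECG output, the SAP text should be brought into line with them.

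**What to change.** Before the first unblinding, do one of the following.

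**Restore the protocol's scope.** Select treatment-emergent CV events of any seriousness from a prespecified list of MedDRA preferred terms or SMQs, as SAP 4.6.3.5.5 does for hypersensitivity. Show MACE/SAE as a labelled subset if wanted. Add an abnormal-ECG summary by arm, with the definition set in advance by the sponsor.

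**Keep the narrow rule openly.** Define MACE for this trial, say which events the medical review covers and by what criteria, label the table and listing as MACE/SAE only, and record and justify the change in the SAP, including the dropped ECG element.

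In either case, align SAP 4.1 with protocol 9.4.1 on where changes are justified, and make 4.9 consistent with the body of the SAP.

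The first option costs one term list, one ECG definition and minor extra programming. It avoids new data collection only if the ECG definition uses what protocol 8.2.3 already provides: machine-read intervals and heart rate, or ECG-related adverse events. The documents do not show a site-entered normal/abnormal ECG field. The second option costs one definition, two relabelled outputs and a few sentences.

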#### **TFLs Related to CV**

Analysis	Additional Information
Summary of Cardiovascular Adverse Events	By Treatment Group and PT
Listing of Cardiovascular Adverse Events	

Abbreviations: PT= preferred term.

#### **4.6.3.5.5. *Hypersensitivity Reactions***

If preferred term is in below list, they are considered as hypersensitivity events:

1. Narrow terms in the Anaphylactic Reaction SMQ (20000021)
2. Narrow terms in the Angioedema SMQ (20000024)
3. Narrow terms in the Severe Cutaneous Adverse Reactions SMQ (20000020)
4. Narrow terms in the Hypersensitivity SMQ (20000214).

#### **TFLs Related to hypersensitivity**

Analysis	Additional Information
Summary of Allergic/hypersensitivity Adverse Events	By Treatment Group and PT
Listing of Allergic/hypersensitivity Adverse Events	

Abbreviations: PT= preferred term.

#### **4.6.3.5.6. *Gastrointestinal***

The events (Constipation, Diarrhoea, Nausea and Vomiting) will be captured by the corresponding PTs. Following TFLs will be created.

#### **TFLs Related to gastrointestinal**

Analysis	Additional Information
Incidence and Prevalence of Gastrointestinal Adverse Events (Constipation, Diarrhoea, Nausea and Vomiting) (Table)	By Treatment Group and Weeks
Time to First Onset of Gastrointestinal Adverse Events (Constipation, Diarrhoea, Nausea and Vomiting) (Figure)	By Treatment Group and Weeks
Duration of Treatment-Emergent Gastrointestinal Adverse Events (Constipation, Diarrhoea, Nausea and Vomiting) (Table)	By Treatment Group and Days

Incidence and prevalence are categorized into the following periods:

Interim analysis (weeks): 0, 4, 8, 12, 16, 20, **26** (4-week interval except the last category)

final analysis (weeks): 0, 4, 8, 12, 16, 20, **24**, 28, 32, 36, 40, 44, 48, 52 (4-week interval)

For example, at the interim analysis, following categories are used:

[0 <= weeks <=4], [4 < weeks <=8] ..., [20 < weeks <=26], [26 < weeks],

Kaplan-Meier analysis will be conducted (censored at the time when patients discontinue study.)

#### **4.6.3.5.7. Acute Gallbladder Disease**

Acute Gallbladder Disease is defined as one of the following conditions (contains both narrow and broad terms):

[1] SMQ= Gallbladder related disorders

[2] SMQ CODE = 20000124

Table and listing will be created.

### **4.7. Other Analyses**

#### **4.7.1. Subgroup analyses**

Subgroup-by-treatment interaction will be tested with 2-sided alpha level of 0.10.

Binary outputs (at Week 26 for interim DBL, at Week 52 for final DBL) will be evaluated based on odds ratio with 95% confidence interval.

##### **4.7.1.1. Efficacy Subgroup Analyses**

Following subgroup will be used:

[SUB1] Baseline HbA1c (%) (2 groups: value < 8.5, 8.5 <= value)

[SUB2] Age subgroup 1 (years) (2 groups: value < 65, 65 <= value)

[SUB3] Age subgroup 2 (years) (3 groups: value < 65, 65 <= value < 75, 75 <= value)

[SUB4] Sex (2 groups: male, female)

[SUB5] Duration of Diabetes (years) (2 groups: value < median, median <= value)

[SUB6] Baseline Body Weight (kg) (2 groups: value < median, median <= value)

[SUB7] Baseline BMI (2 groups: value < 25, 25 <= value)

[SUB8] Monotherapy or OAM combination (2 groups: Monotherapy, SU/BG/a-GI/TZD/Glinides/ SGLT-2i)

Note that the medians are based on ITT population.

For [SUB1]-[SUB8] following analysis will be conducted:

[SUB\_EFF1] Change from baseline in HbA1c (%)

[SUB\_EFF2] Proportion of participants achieving HbA1c target of  $\leq 6.5\%$

[SUB\_EFF3] Proportion of participants achieving HbA1c target of  $< 7.0\%$

[SUB\_EFF4] Change from baseline in body weight (kg)

**Table GBGQ.4.2. Statistical Model Term Summary for the Subgroup Analysis**

	A	B	C	D	E	F	G	H
1		Analysis:	CFB A1c (%)	CFB Weight (kg)	CFB Pulse (bpm)	A1c < 7%, <=6.5%	Nausea, Diarrhoea	Hypo Level 1, Hypo Level 2 (Incidence)
2		Outcome type	Continuous (mult-visits)			Binary (single)	Binary (single)	Binary (single)
3		Model	MMRM			Logistic	Logistic	
4		Basic model (each subgroup)	TMT, BASE, visit, TMT*visit			TMT, BASE	TMT	
5		Basic model (combined subgroup)	TMT, BASE, visit, TMT*visit, SUB, SUB*TMT, SUB*visit, SUB*TMT*visit			TMT, BASE, SUB, SUB*TMT,	TMT, SUB, SUB*TMT,	
6	Subgroup	BASE in the model	A1c (conti.)	Weight (conti.)	Pulse (conti.)	A1c (conti.)	None	
7	SUB1	Term adjust	OAM Delete:BASE	OAM	OAM	OAM Delete:BASE	OAM	
8	SUB2-5	Term adjust	OAM	OAM + A1c(stratum)		OAM	OAM + A1c(stratum)	
9	SUB6/7	Term adjust	OAM	OAM + A1c(stratum) Delete: BASE	OAM + A1c(stratum)	OAM	OAM + A1c(stratum)	
10	SUB8	Term adjust	None	A1c(stratum)		None	A1c(stratum)	

Abbreviation: A1c = hemoglobin A1c; BASE=baseline; CFB = change from baseline; cont. = continuous; Hypo = hypoglycemia; Logistic = logistic regression; MMRM = mixed-effects model for repeated measures; OAM = oral antihyperglycemic medication; SUB = subgroup; TMT = treatment

Two statistical models will be used:

[Model 1] Estimation model for each subgroup (denoted as “each subgroup” in [Table GBGQ.4.2](#)).

[Model 2] Interaction tests model for combined subgroup (denoted as “combined subgroup” in [Table GBGQ.4.2](#)).

Model 1 and Model 2 have different covariates. They are summarized in [Table GBGQ.4.2](#).

Example: [SUB1] [SUB\_EFF3] (A1c <7% analysis) each subgroup model will have

[Model 1] (TMT+BASE) + (OAM -BASE) = TMT +OAM.

[Model 2] (TMT+ BASE+ SUB+SUB\*TMT) + (OAM-BASE) = TMT+SUB+ SUB\*TMT + OAM.

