**[Case 2] Multiple post-baseline time point (e.g., Lab analysis from baseline through Week 52 and follow-up period)**

Change from baseline will be analyzed using mixed model for repeated measures (MMRM). Except for the HbA1c analysis (primary analysis), the model includes

- treatment, baseline value, visit, the interaction of treatment-by-visit, pre-study OAM class, and baseline HbA1c stratum,

as fixed effects.

The HbA1c analysis excludes the HbA1c stratification factor from the MMRM model because HbA1c is included as a continuous baseline variable.

The covariance structure to model the within-participant errors will be unstructured. If the unstructured covariance matrix results in a lack of convergence, the heterogeneous Toeplitz covariance structure, followed by the heterogeneous autoregressive covariance structure will be used. The restricted maximum likelihood (REML) will be used. The Kenward-Roger method will be used to estimate the denominator degrees of freedom.

Type III tests for the LS means will be used for the **treatment comparison**; LS mean difference, SE, p-value, and 95% CI will also be reported. In addition, **within treatment comparison** (the post-baseline value v.s. baseline value) will be conducted with the same model. P-value will be reported.

The same MMRM model will be used to estimate actual value at each visit.

For continuous laboratory analysis, the model specified above will be used for treatment comparison. However, actual visit values and change from baseline are based on descriptive statistics, not from the statistical models (LSmeans). There will be no within treatment comparison.

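### Three sets of subgroup models in Table GBGQ.4.2 drop the continuous baseline value without a stated reason, at a small to moderate cost in precision for the MMRM outcomes

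*SAP*

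**What the plan says.** SAP 4.7.1.1 defines the three subgroup factors concerned: "SUB1] Baseline HbA1c (%) (2 groups: value < 8.5, 8.5 <= value", "SUB6] Baseline Body Weight (kg) (2 groups: value < median, median <= value" and "SUB7] Baseline BMI (2 groups: value < 25, 25 <= value". Table GBGQ.4.2 then adjusts a basic model that contains BASE.

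- SUB1, for HbA1c change and for the two HbA1c targets: "OAM Delete:BASE". Weight and pulse change in SUB1 keep BASE.
- SUB6/7, for weight change only: "OAM + A1c(stratum) Delete: BASE". HbA1c change, the HbA1c targets and pulse change in SUB6/7 keep BASE.

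The worked example below the table, for the <7% target in SUB1, gives "Model 1] (TMT+BASE) + (OAM -BASE) = TMT +OAM" for the model within each subgroup and "TMT+ BASE+ SUB+SUB\*TMT) + (OAM-BASE) = TMT+SUB+ SUB\*TMT + OAM" for the interaction model. The deletion is therefore deliberate.

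The main models differ. SAP 4.1, Case 2, has the baseline value in every MMRM. SAP 4.1 on binary variables has it in the longitudinal model for the HbA1c targets and in the simple logistic fallback. The example in SAP 4.7.1.3 for the OAM subgroups also keeps it. No reason for the three deletions appears in the table or the text around it.

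**The concern.** Dichotomising a baseline variable leaves variation inside each half. Protocol 5.1 admits Visit 1 HbA1c of 7.5-9.5% on a DPP-4i and 8.0-10.0% on another OAM, so baseline HbA1c still varies on either side of 8.5%. BASE and SUB are not collinear and can be fitted together.

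Elsewhere the SAP prefers the finer measure: "The HbA1c analysis excludes the HbA1c stratification factor from the MMRM model because HbA1c is included as a continuous baseline variable". In SUB1 the coarser one displaces the finer. SUB7 is the clearest case, because people of different height and the same BMI differ in weight, yet baseline weight in kg is removed from a model for change in weight.

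At stake are the precision of the subgroup estimates and of the interaction tests (two-sided 0.10, SAP 4.7.1), and whether a subgroup estimate can be read beside an overall estimate that is baseline-adjusted. Protocol 9.4.5 plans the HbA1c and weight subgroup analyses by baseline HbA1c and body weight; the SAP adds the BMI split and the HbA1c targets.

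**Working it through.** **The plan's own figure.** SAP Section 5 assumes 352 and 176 evaluable, difference 0.3, SD 1.0, two-sided alpha 0.05. SE = sqrt(1/176 + 1/352) = 0.0923; 0.3/0.0923 - 1.96 = 1.29; power 90.1%. The stated power of at least 90% reproduces. The plan gives no SE, power or baseline-change correlation for the subgroups.

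**HbA1c change, SUB1.** Inputs from the documents: SD of change 1.0, 176 evaluable controls with 2:1 allocation, 225 of 585 on DPP-4i, the eligibility ranges. Assumed: baseline-change correlation r of 0.2-0.6; Visit 1 HbA1c uniform or right-skewed within its range; Visit 1 to Visit 3 noise SD 0.25. This is a single-visit approximation to the MMRM.

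- slope = r / SD(baseline); residual variance = 1 - r²
- SE ratio (without / with BASE) = sqrt[(1 - r² + slope² × within-group baseline variance) / (1 - r²)]

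Example: uniform, r = 0.4, group ≥8.5%. Baseline SD is 0.674 overall and 0.446 within the group, and 65.3% of participants fall in it.

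- slope = 0.4/0.674 = 0.593; slope² × 0.446² = 0.070; residual variance 0.84
- SE ratio = sqrt(0.910/0.84) = 1.041
- controls = 176 × 0.653 = 114.9; sqrt(1.5/114.9) = 0.1143
- SE with BASE = sqrt(0.84) × 0.1143 = 0.105; without = sqrt(0.910) × 0.1143 = 0.109
- power for 0.3: 82% with BASE, 79% without

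| Baseline shape | r | SE ratio <8.5% | SE ratio ≥8.5% | SE ratio, interaction |
|---|---|---|---|---|
| uniform | 0.2 | 1.004 | 1.009 | 1.006 |
| uniform | 0.4 | 1.020 | 1.041 | 1.027 |
| uniform | 0.6 | 1.058 | 1.116 | 1.079 |
| skewed | 0.2 | 1.006 | 1.008 | 1.007 |
| skewed | 0.4 | 1.027 | 1.037 | 1.033 |
| skewed | 0.6 | 1.079 | 1.106 | 1.094 |

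Dropping BASE from an unsplit analysis would cost 1/sqrt(1 - r²) = 1.02, 1.09 and 1.25. The split already removes much of the baseline spread (SD 0.59-0.67 overall, 0.31-0.45 within groups).

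**Chance imbalance is the same loss.** In the example it moves the subgroup estimate at random with SD sqrt(0.070) × 0.1143 = 0.030, and 0.1047² + 0.0302² = 0.1090², the unadjusted SE squared. Over the whole grid this SD is 0.014-0.052 percentage points, with mean zero under randomization.

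**Weight change, SUB6/7.** Assumed: r of 0.1-0.3, normal weight, weight-BMI correlation 0.8, BMI 25 near the median. The fraction of baseline variance left within groups is 1 - 2/π = 0.363 (SUB6) and 1 - 0.64 × 2/π = 0.593 (SUB7). At r = 0.3 the SE ratio is sqrt[(0.91 + 0.09 × 0.363)/0.91] = 1.018 and sqrt[(0.91 + 0.09 × 0.593)/0.91] = 1.029; at r = 0.1, 1.002 and 1.003.

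**HbA1c <7.0%, SUB1 (logistic).** 1,500 simulated trials per correlation, uniform baseline. Each cell is without / with BASE.

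| r | Group | log OR | SE | power |
|---|---|---|---|---|
| 0.2 | <8.5% | 0.499 / 0.511 | 0.327 / 0.333 | 34.0% / 34.9% |
| 0.2 | ≥8.5% | 0.493 / 0.519 | 0.257 / 0.265 | 48.2% / 49.8% |
| 0.4 | <8.5% | 0.539 / 0.548 | 0.322 / 0.326 | 38.9% / 39.4% |
| 0.4 | ≥8.5% | 0.551 / 0.564 | 0.252 / 0.255 | 59.8% / 60.6% |
| 0.6 | <8.5% | 0.599 / 0.601 | 0.331 / 0.333 | 43.9% / 42.7% |
| 0.6 | ≥8.5% | 0.617 / 0.620 | 0.247 / 0.248 | 70.1% / 70.3% |

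Without BASE the SE is slightly smaller, the log odds ratio is slightly nearer 0, and power moves by less than 2 points.

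**The case against.** The deletion is pre-specified, follows a consistent worked example, and sits in a non-confirmatory section whose details the protocol leaves to the SAP. It could reflect a wish not to carry two versions of one baseline variable. HbA1c information is not absent from SUB1: the interaction model keeps SUB, the other model is fitted within a level of it, OAM class carries some baseline information because eligibility differs by class, and randomization is stratified by Visit 1 HbA1c. All of this stands, and it is why the loss is modest. It does not make BASE redundant. The stratum uses Visit 1 HbA1c and cuts at 9.0% for the non-DPP-4i classes (360 of 585 planned), whereas SUB1 cuts baseline at 8.5% for everyone. None of it bears on weight in SUB7.

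Some stronger readings are tempting, but the documents do not support them.

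- That the deleted term is the strongest covariate in the main analysis: no section reports covariate strength, and baseline weight is not in the primary HbA1c model.
- That every SUB1 and SUB6/7 model is affected: the deletion is specific to the outcomes listed above.
- That the quoted model becomes noisier: it is logistic, where leaving out a covariate changes which odds ratio is estimated and does not raise its SE.
- That chance imbalance biases the estimates, or is a harm on top of the larger SE: it has mean zero and is already inside that SE.

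It is also true that restoring BASE would not fully align the target analyses, since the main one is longitudinal and the subgroup one uses a single visit.

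**Conclusion.** The point holds as a small, unexplained inconsistency with a real but modest cost. For HbA1c change in SUB1 the SE is about 0.4-12% larger, and the interaction SE about 1-9% larger, over assumed baseline-change correlations of 0.2-0.6; the upper end needs 0.6. For weight change the SE is at most about 3% larger at assumed correlations of 0.1-0.3. For the HbA1c targets the issue is comparability: the subgroup odds ratios are not baseline-adjusted while the overall one is, with a slight move towards 1 and almost no change in power. The direction for the MMRM outcomes is secure provided baseline predicts change; the sizes rest on the assumptions above, none of which the documents supply. The primary analysis and its power statement are unaffected.

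**What to change.** In Table GBGQ.4.2, remove the deletion of BASE from the SUB1 cells for HbA1c change and HbA1c targets and from the SUB6/7 cell for weight change. Update the worked example to match:

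- SUB1 Model 1 = TMT + BASE + OAM
- SUB1 Model 2 = TMT + BASE + SUB + SUB*TMT + OAM

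For the MMRM outcomes add the visit terms already in the table. For weight change in SUB6/7 keep baseline weight beside OAM class and the HbA1c stratum. If the sponsor has a reason for the deletion, state it and report the baseline-adjusted version as a check.

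The cost is an edit to three table cells and one example. The covariates are already collected and already in the main models.
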